Clinical signs and symptoms of infection on the target ulcer: Presence or absence of the clinical signs of infection (i.e., redness, swelling, tenderness, heat, purulence) as assessed by the Investigator or confirmed (i.e., microbiological culture) clinical infection, in the target ulcer.

Need for administration of antibiotics: Administration of antibiotics for a target ulcer infection.

Pain on removal of dressing: Subject response to the level of pain as recorded on the VAS during the removal of the NPWT dressing.

Pain on initiation of therapy/during dressing wear: Subject response to the level of pain as recorded on the VAS during the initiation of NPWT therapy (dressing draw-down) and during wear.

Dressing wear time: Time (days) between dressing changes.

Number and reason for dressing changes: Total number of dressing changes over the 12week treatment period and the documented reason for a dressing change.

Closure method: The number of subjects that undergo a surgical intervention (closure by simple flap, Split-Thickness Skin Graft (STSG), delayed primary intention with sutures).

Additional interventions: The number of subjects that require hospital admission, a surgical intervention for a wound related complication, or specialist referral for wound related complication.

Device trouble-shooting: The number and type of device trouble shooting episodes (alarm conditions/device failures/other malfunctions).

Impact of the device on aspects of daily living and satisfaction with device therapy: Subject response to a custom questionnaire to assess the impact of treatment with the device on subject's daily activities and satisfaction with the device.

CONFIDENTIAL DOCUMENT
This document contains confidential information, which is the property of Smith & Nephew, Inc. Do not copy, disclose, or circulate without written authorization from the appropriate Smith & Nephew personnel

SAFETY: Recording of AE associated with the target ulcer and all SAE

PK: NA

Adverse Device Effects:

Both volunteered and elicited

Other:

CONFIDENTIAL DOCUMENT
This document contains confidential information, which is the property of Smith & Nephew, Inc. Do not copy, disclose, or circulate without written authorization from the appropriate Smith & Nephew personnel

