9.1.8 Concomitant Medications

A concomitant medication is any drug or substance administered from Screening Run-in Visit 1 of the study through the last study visit.

Since the ulcer treatments in this study are devices and treat only the target ulcer area covered by the device dressings, with no systemic effects, the only concomitant medications to be reported during this study in the eCRF are as follows:

- All current and past target ulcer treatments only (no doses will be recorded)
- Concomitant medications (no doses to be recorded) used to treat the target ulcer (e.g., systemic antibiotics for a target ulcer infection) and the peri-wound area (such as treatment for erythema, irritation, itching), together with the indication for the medication

- Concomitant medications used to treat all ADE, SADE, and UADE will be recorded in the appropriate eCRF forms

The use of all concomitant therapies must be recorded in the subject's source, together with any associated AE, SAE, ADE, ASADE or UADE, but only reported in the subject's eCRF as described above.

The following concomitant medications are not permitted during the study period:

- Systemic corticosteroids with daily administration of greater than 10 days
- Systemic drugs intended to function as immunosuppressants
- Any target ulcer treatment, excluding study treatment or surgical procedures, specifically intended to close the ulcer
- Topical antibiotics to the target ulcer or to the target peri-wound area
- Mid- to superpotent topical steroids used for > 10 days
- Enzymatic debriders to target ulcer
- Systemic chemotherapy
- Radiation therapy directed to the affected limb
- Current or prior normothermic (Warm-UP®) or HBO therapy within 7 days of the Screening Run-in Visit 1, unless the tissue area has been fully excised

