- The difference between treatments in the change in subject reported Quality of Life (QoL) during the 12-week treatment period. The Health related Quality of Life (HRQoL) will be assessed using the EQ-5D and CWIS validated instruments. Study subjects will complete both instruments at the Randomization Study Visit 1 and at the End of Treatment period. The change in continuous measures of the EQ-5D and CWIS instruments (including Time Trade-off (TTO) index, EQ-VAS, and domain averages) between the randomization Study Visit 1 and End of Treatment period will be derived as follows using the relevant variable:

(Value at End of Treatment period – Value at Randomization Study Visit 1)

Exploratory Endpoints

The exploratory endpoints are as follows:

- Assessment of change in target ulcer progression parameters over the 12-weeks and comparison between treatments including: Estimation of the types of tissue present on the target ulcer, Presence of Infection/Clinical signs of infection, Condition of peri-wound skin, Need for administration of antibiotics and additional interventions, dressing wear time, pain on removal of dressing and at initiation of, and during, therapy.

The subject's target ulcer will be assessed by the Investigator at each study visit. Where possible this assessment will be made using a modified Bates-Jensen wound assessment tool, this will include information concerning presence of Undermining, Necrotic Tissue Type and Amount, Exudate Type and Amount, Granulation Tissue and Epithelialization. Otherwise the Investigator's assessment against a custom descriptive scale will be used.

Condition of peri-wound skin will be assessed by the Investigator against a custom 7-category descriptive scale: Normal, Erythematous, Edematous, Eczematous, Excoriated, Macerated and Indurated. Presence of each skin type will be recorded.

Assessment of the presence of infection and clinical signs of infection will be undertaken by the Investigator.

Presence of Undermining, Necrotic Tissue Type and Amount, Exudate Type and Amount, Granulation Tissue and Epithelialization will be assessed using the modified Bates Jensen wound assessment tool.

Pain associated with removal of dressing, and at initiation of, and during, therapy will be assessed using the Pain VAS scale.

The need for administration of antibiotics and additional interventions in the opinion of the Investigator will be recorded.

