Duration of wear = Date of removal visit – Date of application visit – duration of study therapy interruption

If an unscheduled visit takes place between consecutive assessments multiple duration of wear values will be derived:

Duration of wear 1= Date of unscheduled visit – Date of application study visit

Duration of wear 2= Date of removal study visit – Date of unscheduled visit – duration of study therapy interruption

If more than one unscheduled visit occurs between consecutive assessments, further multiple wear times will be derived as above.

27. The average wear time per patient (patient level) will be derived as follows per subject:

Sum of duration of dressing wear (dressing level) values / Count of duration of dressing wear (dressing level) values

28. The median value for the baseline (Run-In Visit 2/Study Visit 1) target ulcer area will be derived for both the Full Analysis Set and Per Protocol populations by wound type and overall. The median value will also be derived for the depth and volume.

29. Whether or not the reference ulcer is clinically infected at any Study Visit.

30. Whether or not the reference ulcer has signs of infection at any Study Visit.

31. Whether an intervention was required will be derived for each subject:

If an unscheduled visit is recorded, where the reason for intervention is not given as routine: Intervention = Yes

If no unscheduled visits are recorded: Intervention = No

32. Whether prescription of an antibiotic was required will be derived for each subject:

If "have any systemic antibiotics been prescribed" = Yes at any assessment, or any antibiotic medications are recorded on the concomitant medications form, with a start date after randomization: Antibiotic = Yes

Document Number: 1004313

Document Version: 06

Document Part: 000

Document Status: Released

If "have any systemic antibiotics been prescribed" = No at all assessments, and no antibiotic medications are recorded on the concomitant medications form:
Antibiotic = No

33. Whether an intervention or prescription of an antibiotic was required will be derived for each subject:
If Intervention derivation (Derived Variable 31) = Yes or Antibiotic derivation (Derived Variable 32) = Yes, then need for intervention or antibiotic= Yes
If Intervention derivation (Derived Variable 31) = No or Antibiotic derivation (Derived Variable 32) = No, then need for intervention or antibiotic= No

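### SAP item 32 omits the condition that the antibiotic be for a target ulcer infection, so unrelated courses can enter an exploratory between-device test, mainly through the visit question

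*SAP*

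**What the plan says.** The protocol synopsis, under exploratory variables, gives the only explicit definition: "Need for administration of antibiotics: Administration of antibiotics for a target ulcer infection". Protocol 9.4 is looser and names no indication: "The need for administration of antibiotics and additional interventions in the opinion of the Investigator will be recorded". Protocol 10.3.3 also names none.

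SAP 4.3 item 32 derives the flag from two sources joined by OR:

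- the visit question "have any systemic antibiotics been prescribed", answered Yes at any assessment;
- the concomitant medications form: "any antibiotic medications are recorded on the concomitant medications form, with a start date after randomization: Antibiotic = Yes".

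The flag is No when the visit question is No throughout and the form holds no antibiotic at all.

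Protocol 9.1.8 limits what reaches the eCRF: "the only concomitant medications to be reported during this study in the eCRF are as follows". The list covers current and past target ulcer treatments, medications "used to treat the target ulcer (e.g., systemic antibiotics for a target ulcer infection) and the peri-wound area" (recorded "together with the indication for the medication"), and medications for device effects. Other therapies stay in the source documents. Protocol 6.5 permits oral or systemic antibiotics after randomization for an infection that needs treatment, without tying it to the target ulcer.

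Item 33 combines the flag with the intervention flag. SAP 4.11 applies Fisher's exact test to antibiotics alone and to the composite, in the Full Analysis Set.

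**The concern.** The protocol's variable describes how the target ulcer fared under each device. The SAP's variable, read literally, describes whether the subject received a systemic antibiotic. The two separate whenever a subject is treated for an infection elsewhere, or for a non-target ulcer, which the eligibility criteria allow to be present.

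If such courses are counted and are about equally common in both arms, both percentages rise and the difference between devices shrinks. The reported need for antibiotics would then be higher than the quantity the protocol defines, and the tests in SAP 4.11 would be less able to show a real difference.

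**Working it through.** **Which courses each branch can admit**

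| Type of course | Visit question | Concomitant medications form, if sites follow 9.1.8 |
|---|---|---|
| Target ulcer infection | Yes | Yes |
| Peri-wound area, not ulcer infection | Yes | Yes |
| Treatment of a device effect, not ulcer infection | Yes | Possible |
| Chest, urinary, dental or non-target-ulcer infection | Not excluded by the wording | No, unless it treats a device effect |

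The branches are joined by OR, so one Yes to the visit question sets the flag whatever the form holds. The CRF page is not among the documents, so it cannot be seen whether that question sits inside the target ulcer infection assessment.

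**The No rule.** The form branch of the Yes rule requires a start date after randomization; the No rule does not. A subject whose only recorded antibiotic began before randomization, and who answers No at every visit, is neither Yes nor No. This can happen, because 9.1.8 asks for past target ulcer treatments to be recorded.

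**Size of the possible dilution (illustration).** The documents state no antibiotic rate and no power for this variable, so there is no plan figure to reproduce. Inputs, all assumed:

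- true target-ulcer antibiotic rates p of 10% and 25%;
- 75 analysed subjects per arm (the plan randomizes about 80 per arm);
- a proportion u of subjects with an unrelated course that is counted, equal in both arms and independent of ulcer-related use.

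Observed rate = 1 − (1 − p)(1 − u), so the risk difference becomes (1 − u) times the true one. For u = 5%: 1 − 0.90 × 0.95 = 14.5% and 1 − 0.75 × 0.95 = 28.75%; the difference is 14.25 points = 0.95 × 15. Power is by exact enumeration of the two-sided 5% Fisher test.

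| u | Observed rates | Difference (points) | Odds ratio | Fisher power |
|---|---|---|---|---|
| 0 | 10.0% v 25.0% | 15.0 | 3.00 | 61% |
| 2% | 11.8% v 26.5% | 14.7 | 2.70 | 56% |
| 5% | 14.5% v 28.75% | 14.25 | 2.38 | 49% |
| 10% | 19.0% v 32.5% | 13.5 | 2.05 | 40% |

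With other assumed rates at 80 per arm the pattern is the same. For 10% v 30%, power goes from 86.7% (u = 0) to 82.8%, 76.6% and 66.4% at u = 2%, 5% and 10%. For 15% v 35%, it goes from 79.9% to 76.2%, 70.8% and 62.9%.

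**The case against.** A reader might infer that item 32 counts antibiotics given for any reason and that the comparison is therefore diluted. The documents do not support that.

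- **The form is already restricted.** Under 9.1.8 a chest, urinary or dental course should not reach the concomitant medications form unless it treats a device effect. SAP 4.13 likewise summarizes only concomitant medications relevant to the target ulcer. This stands, and it removes most of the exposure from that branch.
- **The visit question's context is unknown.** It may be asked only about the target ulcer. This also stands, so leakage is possible but not shown. The SAP as written still sets no limit, and an analysis rule should not depend on a form layout it does not state.
- **The protocol is not uniform.** Only the synopsis states the indication. That makes the gap partly one of clarification. However, 9.4 lists the item among target ulcer progression parameters, which agrees with the synopsis.
- **The power figures rest on assumed rates.** True. A high rate of unrelated courses has no source in the documents, and 9.1.8 makes low values more plausible.
- **Little is at stake.** The endpoint is exploratory. Target ulcer infection is derived separately (items 29 and 30) and incidence of infection has its own Fisher test in SAP 4.11, so a difference in ulcer infection would not be hidden by item 32.

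**Conclusion.** The concern holds in a limited form. Item 32 lacks the indication condition in the protocol's only explicit definition, and the resulting flag is tested between devices, alone and in the composite. The exposure lies mainly in the visit question; the form branch can add peri-wound and device-effect courses.

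Dilution is possible, not established. Its direction is firm if unrelated courses are equally common in both arms and independent of ulcer-related use. Its size cannot be determined from the documents. In the illustration at 75 per arm, 2% unrelated use costs about 5 points of power and 10% costs about 21. Severity is low: the primary, key secondary and secondary conclusions are unaffected.

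**What to change.** Amend SAP 4.3 and 4.11 as follows.

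1. Item 32, Yes rule: Antibiotic = Yes only if a systemic antibiotic started after randomization with target ulcer infection as its indication, using the indication collected under Protocol 9.1.8.
2. Reconcile every Yes to the visit question against the concomitant medications form before coding. A target-ulcer course that is missing from the form is then queried and not set to No.
3. Item 32, No rule: apply the same indication and start-date conditions, so that every reconciled subject is either Yes or No.
4. Carry the revised flag into item 33 and the Fisher tests in SAP 4.11.
5. State the scope of the visit question. If use for any indication is reported, give it descriptively from that question only, since the form is not meant to hold unrelated medications.

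The cost is a few lines of SAP wording and programming, plus data queries for unmatched visit answers. No new data item is needed, because the indication is already collected for target ulcer medications.

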This document contains confidential information, which is the property of Smith & Nephew, Inc. Do not copy, disclose, or circulate without written authorization from the appropriate Smith & Nephew personnel

CONFIDENTIAL DOCUMENT
This document contains confidential information, which is the property of Smith & Nephew, Inc. Do not copy, disclose, or circulate without written authorization from the appropriate Smith & Nephew personnel.

5. Remove NPWT topical dressing to assess the target ulcer.
6. Assess level of pain, post NPWT dressing removal, using the VAS.
7. Complete reason for dressing change assessment and record any additional dressing changes since previous assessment as an unscheduled visit.
8. Assess target ulcer and record if target ulcer is closed or if target ulcer is ready for and will be surgically closed.

Note 1: If the target ulcer is closed, skip procedures 9-15 and complete procedure 16.

Note 2: If target ulcer is ready for and will be surgically closed, skip procedures 9-16 and complete procedure 17.

9. Examine the ulcer for evidence of infection, and treat the infection as appropriate per local protocol.
10. Debride the ulcer if indicated, at the discretion of the Investigator.
11. If the target ulcer remains open, photograph and determine the post-debridement ulcer area (cm²), perimeter (cm), greatest depth (mm), volume (cm³), and maximum linear dimension (cm) using the ARANZ Silhouette wound imaging and measurement device if applicable.

If debridement is not performed, an image of the target ulcer is still required to determine the ulcer area (cm²), perimeter (cm), greatest depth (mm), volume (cm³) and maximum linear dimension (cm) using the ARANZ Silhouette wound imaging and measurement device.

12. Conduct an ulcer assessment using the modified Bates-Jensen wound assessment tool and record percentage tissue type/condition of peri-wound skin assessment (Normal, Erythematous, Edematous, Eczematous, Excoriated, Macerated, Indurated).
13. Re-application of investigational product (PICO) or comparator tNPWT system

according to randomization schedule.

Record any additional dressings used and rationale for using this dressing.

Type of wound filler dressing if used (foam or gauze-based filler dressing).

Number of personnel used to apply NPWT system.

Time used to apply NPWT system (minutes).

Record level of negative pressure, intensity setting and delivery mode selected for tNPWT subjects, if appropriate for device selected.

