4.3 Derived Data

1. A flag for patient inclusion in the full analysis set. If the patient has received NPWT and has at least one (post-baseline) dressing change assessment then the patient is included in the full analysis set. Otherwise the patient is excluded from the full analysis set.
2. A flag for patient inclusion in the safety population. If the patient has received NPWT, then the patient is included in the safety population. Otherwise the patient is excluded from the safety population.
3. The duration in days between the baseline assessment (Randomization Study Visit 1) and each scheduled Study Visit (2-12) (scheduled every 7 days) and Study Visit 13 or 14.

ST:

9 7 5

Reference:

CE/052/PIC

Customer Code:

0 5

4. The duration in days between the Screening Run-In Visit 1 and Screening Run-In Visit 2.
5. A flag for whether the Screening Run-In Visit 2 occurred 7 (± 1) days after Screening Run-In Visit 1.
6. The duration in days between the baseline assessment (Randomization Study Visit 1) and each scheduled Study Visit (2-12) (scheduled every 7 days) and Study Visit 13/14.
7. A flag for whether study visits occurred weekly after the Randomization Visit as per the protocol. A separate flag should be derived for each study visit.
E.g. Study Visit 2 should occur at 7 (± 1) days after the Randomization Study Visit 1. Study Visit 3 should occur at 14 (± 1) days etc.
8. The duration in days between the Study Visits i and j (where $i \geq 1$ and $j = i + 1$)
9. Patient age (years) defined as: The date of the baseline assessment – date of birth/365.25
10. Patient body mass index defined as: $\text{Weight (kg)} / (\text{Height (cm}/100))^2$
11. Reference wound duration at point of randomisation will be derived as follows:
Date of Target onset date - Date of Randomization Visit 1
12. The (post-screening) study duration (in days) will be derived as follows:
Date of Study Completion - Date of Randomization Visit 1
13. The Screening duration (in days) will be derived as follows (separately for screening, re-screen 1 and re-screen 2 where appropriate):
Date of Run-In Visit 2 - Date of Run-In Visit 1
14. The number of screening periods per subject will be derived as:
No re-screening periods used = 1
A single re-screening period used = 2
Two re-screening periods used = 3

Document Number: 1004313
Document Version: 06

Document Part: 000
Document Status: Released

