34. All pain assessments (dressing removal, during wear, on initiation of therapy) will be derived as follows:
In cases where pain = No, the VAS pain value will be coded as 0
35. Level of Exudate (amount) will be coded as follows- In cases where Exudate presence=No, then the level/amount of exudate will be coded as None.
36. The responses to the aspects of the wound assessment tool (BWAT-M); Undermining, Necrotic Tissue Type, Necrotic Tissue Type, Necrotic Tissue Amount, Exudate Type, Exudate Amount, Skin Color Surrounding Wound, Granulation Tissue and Epithelialization will be coded at each study visit as defined in Section 7. The individual coded values will then be summed at each individual study visit to give a total wound status score.
37. The personnel time taken at each Study Visit will be derived as:
No. of personnel applying the dressing x time taken to apply the NPWT system
38. The total personnel time taken at throughout the study will be the sum of the personnel time at Study Visits per subject.
39. The duration for which compression therapy was interrupted at each Study Visit in hours will be derived as: hours + (daysx24). If no interruption is recorded then the number of hours will be coded as 0.

ST:

9 7 5

Reference:

CE/052/PIC

Customer Code:

0 5

40. The duration for which study therapy was interrupted at each Study Visit in hours will be derived as: hours + (daysx24). If no interruption is recorded then the number of hours will be coded as 0.
41. The total duration (in hours) for which compression therapy was interrupted per subject will be calculated as the sum of the interrupted duration at each Study Visit.
42. The total duration (in hours) for which study therapy was interrupted per subject will be calculated as the sum of the interrupted duration at each Study Visit.
43. In cases where the ulcer is recorded as closed in the investigators opinion the following imputations will be made if missing values are present:
- Presence of infection = No
 - Presence of clinical signs of infection = No
 - Level of Exudate = None/No
 - Extent of undermining = None
 - Necrotic tissue present = No
 - Epithelialization at target ulcer = 100% wound covered, surface intact
44. Individual flags for whether each event was a serious adverse event, severe adverse event, investigational device related adverse event, a serious investigational device related adverse event, an unexpected adverse event and a serious unexpected adverse event.

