5. Whether or not the adverse event is expected or unexpected.

Document Number: 1004313
Document Version: 06

Document Part: 000
Document Status: Released

ST:

9 7 5

Reference:

CE/052/PIC

Customer Code:

0 5

Clinical Laboratory Evaluations

The subject blood biochemistry and hematological values, including the numbers of subjects that are below (abnormal), within and above (abnormal) the normal ranges, upon entry to the screening period will be summarized.

Hematology: Red Blood Cell (RBC) count, Hemoglobin, Hematocrit, Platelets, White Blood Cell (WBC) total count, and differential (%) including absolute counts (x 10⁹/L)

Blood Biochemistries: Sodium, Potassium, Calcium, Creatinine, Total Bilirubin, ALT, AST, Alkaline Phosphatase, Albumin, Total Protein, Urea, Glucose, and HbA1c

Additional Chemistries: Pre-albumin

Vital Signs, Physical Findings

The vital signs recorded upon entry to the screening period (including Resting Heart Rate, Respiratory Rate, Blood pressure (systolic and diastolic) and Blood pressure measurement location will be summarized.

Concomitant Medications

The number and percent of subjects that take pre-randomization concomitant medications relevant to the target ulcer will be summarized. The number and percent of subjects who take post-randomization concomitant medications relevant to the target ulcer will be summarized separately for new and existing concomitant medications.

5 References

Lan, KKG and DeMets, DL 1983. *Discrete sequential boundaries for clinical trials*. Biometrika; 70: 659-663.

Mark D. Rothmann, 2011. *Design and Analysis of Non-Inferiority Trials (Chapman & Hall/CRC Biostatistics Series)*. 1 Edition. Chapman and Hall/CRC.

Document Number: 1004313

Document Version: 06

Document Part: 000

Document Status: Released

6 How to Score EQ-5D-5L

The EQ-5D-5L descriptive system should be scored, for example, as follows:

Levels of perceived problems are coded as follows:			
Under each heading, please tick the EQ-5D box that best describes your problem (10000)			
MOBILITY			
I have no problems in walking about			
I have slight problems in walking about			
I have moderate problems in walking about			
I have severe problems in walking about			
I am unable to walk about			
SELF CARE			
I have no problems washing or dressing myself			
I have slight problems washing or dressing myself			
I have moderate problems washing or dressing myself			
I have severe problems washing or dressing myself			

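### Several SAP 4.3 derivations (items 32, 36/43 and 11, and in minor ways 9) give missing or wrong values if programmed as written; the effect is confined to exploratory, descriptive and covariate outputs

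*SAP*

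**What the plan says.** All of the derivations are in SAP 4.3.

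- **Item 32 (antibiotic flag).** Yes follows from a positive answer on systemic antibiotics at any assessment, "or any antibiotic medications are recorded on the concomitant medications form, with a start date after randomization: Antibiotic = Yes". No requires "No at all assessments, and no antibiotic medications are recorded on the concomitant medications form". SAP 4.11 uses the flag in Fisher tests, alone and combined with interventions (item 33).
- **Items 36 and 43 (total wound score).** Item 36 sums the BWAT-m codes at each visit and lists "Undermining, Necrotic Tissue Type, Necrotic Tissue Type, Necrotic Tissue Amount, Exudate Type, Exudate Amount" and three more. Item 43 imputes infection, signs of infection, exudate level, undermining, presence of necrotic tissue and epithelialization for a closed ulcer. Protocol 9.1.4 says "If the target ulcer is closed, skip procedures 9-15 and complete procedure 16", and the tool is procedure 12. At Visit 14 (Protocol 9.1.6) it is completed only for ulcers that stayed open or re-opened. SAP 4.11 summarizes the total by visit, at discontinuation and at one-week confirmation.
- **Item 11 (ulcer duration).** "Date of Target onset date - Date of Randomization Visit 1".
- **Item 9 (age).** The formula is "The date of the baseline assessment" minus date of birth/365.25, without brackets.

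**The concern.** In item 32 the start-date condition is on one side only, so the two rules do not cover all subjects. In items 36/43 the sum needs eight codes, but the closure rule supplies fewer, and one-week confirmation is the visit where successfully closed ulcers have no tool recorded. In both places a programmer has to invent a rule. The trial is open-label and the sponsor does the analysis, so that rule is better fixed in advance. Item 11 subtracts a later date from an earlier one, for a covariate that is forced into every primary and secondary regression model and whose effect is to be reported. Item 9, read by the usual order of operations, does not produce an age.

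At stake are the denominator of an exploratory test, the meaning of a descriptive score over time, and the direction of one reported covariate effect.

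**Working it through.** The plan states no figure to reproduce here. Each rule was followed literally.

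**Item 32.**

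| Assessments | Antibiotic on form | Yes rule met | No rule met | Value |
|---|---|---|---|---|
| all No | none | no | yes | No |
| all No | only before randomization | no | no | undefined |
| all No | only on the day of randomization | no | no | undefined |
| all No | any after randomization | yes | no | Yes |
| any Yes | any pattern | yes | no | Yes |

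Item 33 uses OR in both branches. With item 32 undefined, the composite is Yes if item 31 is Yes and No if item 31 is No. It is undefined only if item 31 is undefined too. That can happen: item 31 has no rule for a subject whose only unscheduled visits were routine, and Protocol 9.1.7 has the 2-3 day dressing changes of filler and tNPWT users captured as unscheduled visits.

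**Items 36/43.** Codes available for an ulcer closed without planned surgical closure at that visit, or still closed at Visit 14:

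| Component | Strict reading | Generous reading |
|---|---|---|
| Undermining | 1 | 1 |
| Necrotic type | none | 1 |
| Necrotic amount | none | 1 |
| Exudate type | none | 1 |
| Exudate amount | 1 | 1 |
| Skin color | none | none |
| Granulation | none | none |
| Epithelialization | 1 | 1 |
| Components coded / partial sum | 3 / 3 | 6 / 6 |

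The scale runs from 8 × 1 = 8 to 8 × 5 = 40. An ordinary sum is missing; a sum that ignores missing values gives 3 or 6, below the minimum. SAP 2.3.5 adds LOCF, but only for remaining values analysed at the end of the 12 weeks. There, on the generous reading, carrying forward granulation and skin color (1 to 5 each) gives 6 + 1 + 1 = 8 up to 6 + 5 + 5 = 16. A closed ulcer can therefore carry an open ulcer's granulation score, although the tool has a code of 1 for intact skin.

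**Item 11.** Entry limits are 4 to 104 weeks for VLU and 4 to 52 weeks for DFU. As written, 4 weeks gives -(4 × 7) = -28 days, 52 weeks gives -364 and 104 weeks gives -728. These take the limits as of randomization; if they apply at screening, the run-in adds about 7 days in size. Replacing a covariate D by -D changes only the sign of its own coefficient. An illustrative linear model (n = 160, SD 24.5; distributions of duration, age and enrolment date assumed) gave a treatment estimate of -0.53 (95.4% CI -9.59 to 8.54) both ways, while the duration slope went from 0.0146 to -0.0146 per day. In the logistic and Cox models the ratio becomes its reciprocal: an assumed odds ratio of 0.98 would print as 1/0.98 = 1.02.

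**Item 9.** In SAS day numbers, 1 January 2016 is 20454 and 1 January 1956 is -1461. As written: 20454 - (-1461/365.25) = 20454 + 4 = 20458. With brackets: (20454 + 1461)/365.25 = 60.0. In the same simulated data the literal value correlated 0.998 with enrolment date and 0.18 with true age.

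**Duplicate in item 36.** Nine terms would give 9 to 45 instead of 8 to 40.

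**The case against.** The strongest reply is that these are drafting slips with little reach, and that larger consequences one might infer do not follow. Much of this stands.

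- **Composite.** A reader might infer that subjects without an antibiotic value also leave the combined test. Item 33 still gives them a value unless item 31 is undefined as well.
- **Number affected.** A reader might infer that such subjects are certain to exist, since SAP 4.13 says "The number and percent of subjects that take pre-randomization concomitant medications relevant to the target ulcer will be summarized" and Protocol 9.1.8 lists "All current and past target ulcer treatments only (no doses will be recorded" for the eCRF. Neither is specific to antibiotics. Target-ulcer infection is an exclusion at screening and before randomization, SAP 4.8 summarizes previous treatments separately, and the CRF was not supplied. The gap is possible; its size is unknown.
- **All closed ulcers.** A reader might infer that every closure visit lacks a score. Ulcers going to surgical closure do have the tool completed at that visit (Protocol 9.1.4, procedure 17; Protocol 9.1.5, procedure 10).
- **Hidden benefit.** A reader might infer that an arm with more closures would show no advantage. The total is only summarized, not tested, and closure is compared directly as a secondary endpoint. What remains is that the by-visit and confirmation means rest on ulcers that are not closed.
- **Clerical items.** SAP Section 7 lists the eight components once each, so a 9 to 45 scale is not a realistic outcome. Item 9 is labelled in years, and a value above 20,000 would be noticed. Items 12 and 13 subtract the earlier date from the later, so the intent of item 11 is clear.

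The reply does not remove the gaps in items 32 and 36/43. There the intended value cannot be read off the text with certainty, least of all for skin color.

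**Conclusion.** The point holds as a minor one.

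- **(a) Item 32** leaves an undefined value that feeds an exploratory antibiotic-only test.
- **(b) Items 36/43** leave the total missing, or below the scale minimum, for ulcers closed without planned surgical closure at that visit and for ulcers still closed at Visit 14. At end of treatment LOCF may instead carry open-ulcer scores. The output is descriptive.
- **(c) Item 11** reverses the sign of the reported duration effect and distorts the baseline summaries and the Kaplan-Meier duration categories.
- **(d) Item 9 and the duplicated name** are close to clerical.

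A reader might infer a threat to the primary result. Item 11 provably leaves the treatment estimate, its interval and the non-inferiority conclusion unchanged. Item 9 could reach the primary model only if coded literally, because age is a forward-selection candidate; in the simulated data, including true age gave a treatment estimate of -0.39 (95.4% CI -9.44 to 8.67) and the literal value gave -0.54 (-9.70 to 8.63).

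The conclusions assume literal programming. Those figures depend on assumed distributions and are illustrative only.

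**What to change.** - **Item 32:** No = a negative answer at all assessments and no antibiotic on the form with a start date after randomization. State how a start on the day of randomization is treated; under this wording it counts as No. Check item 31 at the same time for subjects with only routine unscheduled visits.
- **Items 36/43:** list the eight components once. For a closed ulcer, keep the three existing codes, set granulation, necrotic type, necrotic amount and exudate type to 1, and set skin color by a stated rule, for example the last recorded value. The closed total is then 7 + skin color, that is 8 to 12. Two alternatives are less good. Recording skin color at closure adds a protocol procedure. Forcing the total to 8 assumes normal skin color, although Protocol 4.1 describes hemosiderin deposits in venous disease and the tool scores hyperpigmented skin as 5.
- **Item 11:** randomization date minus onset date.
- **Item 9:** (baseline date - date of birth)/365.25.

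The cost is a few lines of SAP wording. Visits, procedures, sample size and the primary analysis do not change.
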